### 11.4. LABORATORY EVALUATIONS

All samples will be analysed at the central laboratory for the study on behalf of AstraZeneca.

The study plan shown in Table 9 lists the variables that will be measured for routine haematology, serum chemistry, coagulation, and urinalysis. All summaries of haematology, coagulation, and chemistry will be based on the results of Standard International (SI) system of units. Unit conversion will be performed according to the Data

## Statistical Analysis Plan

Management Plan (DMP) prior to the transfer to Biostatistics. The indication of clinically significant laboratory results will be recorded on the CRF page. The high and low classifications will be derived relative to the result and normal ranges in SI units.

Summary tables for haematology, coagulation, chemistry and urinalysis (pH, specific gravity) laboratory variables will include the following: descriptive statistics for SI values and change from baseline for all continuous variables by visit and treatment group. Shifts from baseline to maximum post-baseline for CTCAE grades and laboratory reference ranges will be reported for each laboratory parameter.

For urinalysis parameters, any qualitative assessments will be summarized for all patients using the number of patients with results of negative, trace, or positive.

All laboratory results in original and SI units will be presented in data listings and presented graphically as box plots and shift plots. Tests will be listed in alphabetical order within their respective panels (haematology, clinical chemistry, urinalysis). Abnormal values will be flagged.

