an important identified risk. Reduced haemoglobin/anaemia and reduced absolute neutrophil count/neutropenia are important potential risks. When AZD9150 is given in combination with durvalumab, there is a potential for increased frequency and/or magnitude of liver enzymes (since AST/ALT increase is an identified overlapping adverse drug reaction for both drugs; referred to as increased frequency of immune reactions in combination with durvalumab). Risks associated with other combination drugs in recently initiated studies, or studies in course of being initiated (including for example acalabrutinib, or different chemotherapy agents) are yet unknown. For a complete characterisation of each risk, see Section 6 of the IB for AZD9150, Summary of data and guidance for the Investigators.

Effects on blood neutrophils, including reduction in their number (neutropenia) is an identified risk with AZD5069. These effects have been observed at mild levels in healthy volunteers' studies. Across all respiratory studies, now completed, events suggestive of this risk occurred at both mild, moderate, but also 1 severe occurrence (event that was considered serious by the Investigator). In the ongoing D5660C00004 oncology trial so far, although reductions in peripheral blood neutrophil counts have been observed, these have been reversible, not associated with significant clinical symptoms, and not considered serious by the Investigators. Therefore, for regulatory reporting purposes that consider seriousness, events suggestive of this risk are considered expected in patients treated in respiratory indications only, and not yet in the oncology population. Host defence (infections) is a potential risk for AZD5069. However, while reduction of neutrophils in peripheral blood or sputum could have an impact on host defense with regard to infections, previous studies with AZD5069 in healthy subjects and in patients with chronic obstructive pulmonary disease, bronchiectasis, and asthma did not show an increased rate of overall infections compared with placebo. For a complete list of potential risks and their characterisation, see Section 6 of the IB for AZD5069, Summary of data and guidance for the Investigators.

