5.4.1 Laboratory safety assessments

All blood samples will be analyzed at the central laboratory for the study on behalf of AstraZeneca. On days of study drug administration, to shorten the time between the blood draw and the decision if dosing may proceed, blood samples for routine haematology and serum chemistry safety assessments are to be drawn and split into 2 samples: one portion of the sample is to be analysed locally to determine toxicity prior to dosing, and the second portion of the sample is to be sent to the designated central laboratory.

Samples are not to be split on days where no study drug administration is scheduled. See Study Plan (Section 5.2, Table 5) for details.

Blood samples for routine haematology and serum chemistry safety assessments will be obtained at screening; before dosing on Day -7 of the lead-in; before dosing on Days 1, 8, 15, and 22 of Cycle 1; before dosing on Days 1 and 15 of all subsequent cycles; and at the EOT visit.

Blood samples for routine coagulation assessments will be obtained at screening; before dosing on Day –7 of the lead-in; before dosing on Days 1 and 15 of Cycle 1; before dosing on Day 1 of all subsequent cycles; and at the EOT visit.

Urine samples for routine urinalysis will be obtained at screening; before dosing on Day –7 of the lead-in; before dosing on Days 1 and 15 of Cycle 1; before dosing on Day 1 of all subsequent cycles; and at the EOT visit.

The study plan shown in [Table 9](#) lists the variables that will be measured for routine haematology, serum chemistry, coagulation, and urinalysis.

In addition, thyroid function tests are required at screening, before dosing on Day –7 of the lead-in, before dosing on Day 1 of each cycle, and at the EOT visit. Thyroid function tests include thyroid-stimulating hormone and free T3 and T4.

Blood samples for HIV, HBV, and HCV serology are required at screening. The eligibility of patients who have active infection for HIV, HBV, and/or HCV is at the discretion of the Investigator. HIV screening will be based on an FDA-approved antigen/antibody combination immunoassay; HBV screening will include HBsAg, anti-HBc, and anti-HBs, and HCV screening will be based on anti-HCV. HPV status will be collected at screening visit.

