6.4.6 Adverse events based on examinations and tests

The results from the CSP mandated laboratory tests and vital signs, ECGs, and other safety assessments will be summarised in the CSR. Deterioration as compared to baseline in protocol-mandated parameters should therefore only be reported as AEs if they fulfil any of the SAE criteria or are the reason for discontinuation of treatment with the IP.

If deterioration in a laboratory value/vital sign is associated with clinical signs and symptoms, the sign or symptom will be reported as an AE and the associated laboratory result/vital sign will be considered as additional information. Wherever possible the reporting Investigator uses the clinical, rather than the laboratory term (e.g., anaemia versus low haemoglobin value). In the absence of clinical signs or symptoms, clinically relevant deteriorations in nonmandated parameters should be reported as AE(s).

Deterioration of a laboratory value, which is unequivocally due to disease progression, should not be reported as an AE/SAE.

Any new or aggravated clinically relevant abnormal medical finding at a physical examination as compared with the baseline assessment will be reported as an AE.

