Exposure to IP (i.e., total amount of study drug received) will be listed for all patients by cohort.

Total exposure (date of last dose minus date of first dose + 1) and total time on study (date of discontinuation minus date of first dose + 1) will be summarised by the following: Mean, standard deviation, minimum, maximum, median, and number of observations. In addition, the number and percentage of patients with at least 1 dose interruption/dose delay and at least 1 dose-reduction will be presented separately for the initial period of evaluability defined as 28 days and for any time following this initial period of the study.

Relative dose intensity and percentage intended dose for AZD9150, AZD5069, and MEDI4736 will be derived and summarised by the following: Median, minimum, maximum, 75th percentile, 25th percentile, and number of observations. Relative dose intensity is the percentage of actual dose intensity delivered relative to the intended dose intensity through treatment discontinuation. The entire intended treatment period will be used in the derivation of relative dose intensity.

Safety

No inferential testing will be performed on safety data. Safety data will be summarised using descriptive statistics. At the end of the study, appropriate summaries of all safety data will be produced, as defined below.

AEs will be listed individually by patient and treatment group. For patients who have a dose modification, all AEs (due to drug or otherwise) will be assigned to the associated initial dose combination/treatment dose.

AESIs will also be summarised and listed separately for each compound.

The number of patients experiencing each AE will be summarised by the Medical Dictionary for Regulatory Activities (MedDRA) system organ class, MedDRA preferred term and CTCAE grade. The number and percentage of patients with AEs in different categories (e.g., causally related, CTCAE ≥ 3) will be summarised by dose group, and events in each category will be further summarised by MedDRA system organ class and preferred term, by cohort (as appropriate). SAEs and other significant AEs will be summarised separately if a sufficient number occur.

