## Statistical Analysis Plan

For summaries of AEs by SOC and PT, a patient will be counted once at the SOC level and once at each PT within the SOC level. For summaries by SOC, PT, and maximum intensity, a patient will be counted once at the highest intensity level for which the event occurred at the SOC level and the highest intensity level for each unique PT within that SOC level. Therefore, patients may only contribute once to each PT and once to each SOC level.

The summaries presenting frequency of AEs by SOC and PT will be ordered by overall descending frequency of SOC and then, within an SOC, by overall descending frequency of PT.

During the evaluation of the AE data, an INC medically qualified expert will review the list of AEs that were not reported as SAEs and AEs leading to discontinuation of investigational product. Based on the expert's judgment, AEs of particular clinical importance may, after consultation with the Global Safety Physician, be considered other significant AEs (OAEs) and reported as such in the CSR.

The following AE tables will be provided:

- An overall summary of the number and percentage of patients reporting AEs, treatment-related AEs, serious AEs, < Grade 3 or  $\geq$  Grade 3 AEs, AEs considered to be DLTs (see Protocol Section 5.3.2. for definition of DLTs), AEs leading to dose withdrawn, and fatal AEs.
- AEs by SOC and PT
- Most common AEs (i.e., frequency  $\geq$  5%) by PT
- Serious AEs, by SOC and PT
- DLTs
- Study-treatment-related AEs, by SOC and PPT
- Causality Related AEs by CTCAE Grade
- AEs by CTCAE Grade, by SOC and PT
- AEs leading to death, by SOC and PT
- AEs < grade 3 or  $\geq$  grade 3, by SOC and PT

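### The SAP's safety outputs omit the AESI summaries that the protocol requires per compound, shift laboratory reference ranges only to the maximum value, and plan no summary of the thyroid tests

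*SAP*

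**What the plan says.** **AESIs.** Protocol 8.10 (Safety) states: "AESIs will also be summarised and listed separately for each compound". Protocol 6.3 names neutrophil effects, infections and ECG abnormalities as AESIs for AZD5069, and says that AZD9150 currently has none. Protocol 6.9.6 and Appendix H give the immune-mediated categories for MEDI4736; those in 6.9.6 also cover its use with tremelimumab. SAP 11.3 introduces its list with "The following AE tables will be provided". The list has 16 entries, and the only one built around a medical topic is bleeding.

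**Laboratory shifts.** SAP 11.4 says: "Shifts from baseline to maximum post-baseline for CTCAE grades and laboratory reference ranges will be reported for each laboratory parameter". Just before that it says: "The high and low classifications will be derived relative to the result and normal ranges in SI units". It also plans by-visit values and changes from baseline, box plots, shift plots, and listings with abnormal values flagged.

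**Thyroid tests.** Protocol 5.4.1 says that "thyroid function tests are required at screening", and also before dosing on Day -7, on Day 1 of each cycle and at end of treatment. The tests are TSH, free T3 and free T4. SAP 11.4 refers to its Table 9, which "lists the variables that will be measured for routine haematology, serum chemistry, coagulation, and urinalysis". No thyroid test is in that table. Protocol 6.4.6 says: "The results from the CSP mandated laboratory tests and vital signs, ECGs, and other safety assessments will be summarised in the CSR".

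**The concern.** Safety is part of the Part A primary objective (Protocol 2.1) and a Part B objective (Protocol 2.3). Protocol 1.3.2 puts falls in blood counts and immune-mediated disease among the main drug risks. For AZD9150 it says: "Reduced haemoglobin/anaemia and reduced absolute neutrophil count/neutropenia are important potential risks". For MEDI4736 it names under- and overactive thyroid, and TSH change in both directions.

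Three questions depend on the SAP tables:

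- How many patients in an arm had any event in a given AESI category, and at what grade?
- How many patients fell below the normal range on a test after starting treatment?
- How many developed abnormal thyroid results without symptoms?

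With the outputs as specified, no table answers the first or third question directly. The second is answered only for tests with a CTCAE grade in the low direction. The AESI omission is also an undeclared departure from a stated protocol output.

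**Working it through.** The plan states no figure on this point, so the check sets the texts side by side and adds one small illustration.

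**1. AESIs**

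- Required by Protocol 8.10: a summary and a listing for each compound.
- Planned in SAP 11.3: 16 table entries, covering overall counts, SOC and preferred term, common events, SAEs, DLTs, relatedness, CTCAE grade, deaths, withdrawals, dose reductions, other significant AEs, the lead-in period and bleeding. The extra listings concern DLTs. None is an AESI output.
- Declared in SAP 13: only the wording of the PK, PD and efficacy analysis sets.
- Can the existing tables supply the count? Not directly. Under SAP 11.3 a patient counts once for each preferred term. A patient with two terms in one category, for example two endocrinopathies, is in two rows, so the rows cannot be added to give patients with any event in that category.
- Other significant AEs are chosen by expert judgement after review, not by the protocol's AESI definition.
- SAP 11.9 compares immune-related AEs by anti-drug antibody status, but the SAP never defines that set. That analysis needs the same grouping.

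**2. Reference-range shift**

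Read literally, the post-baseline category is that of the highest post-baseline value. A patient is then Low only if every post-baseline value is below the lower limit.

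Illustration with assumed platelet values and an assumed normal range of 150 to 400 × 10⁹/L. The grade 3 and grade 4 limits, below 50 and below 25, are those in Protocol 7.7.3.

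| Patient | Baseline | Post-baseline | Shift to maximum | Shift to minimum |
|---|---|---|---|---|
| A | 220 | 180, 45, 210 | Normal to Normal (210) | Normal to Low (45) |
| C | 300 | 290, 310, 420 | Normal to High (420) | Normal to Normal (290) |

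For patient A the value 45 lies between 25 and 50, so the maximum CTCAE grade is 3, and the grade shift records the fall that the reference-range shift misses. For a test with the same pattern but no CTCAE grade for low values, Normal to Normal would be the only shift result.

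For a test graded in both directions, a single maximum grade gives the severity but not whether the value was high or low.

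**3. Thyroid tests**

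- Collected: screening, Day -7, Day 1 of each cycle, end of treatment (Protocol 5.4.1 and Table 5).
- Summarised: haematology, coagulation, chemistry and urinalysis (SAP 11.4). The sentence ordering the listings names haematology, clinical chemistry and urinalysis.
- AE route: under Protocol 6.4.6, deterioration in a mandated test is an AE only if it meets a seriousness criterion or causes discontinuation; otherwise only accompanying signs or symptoms are reported. The stated reason is that the test results will be summarised in the CSR.
- Result: a thyroid change without symptoms that is not serious and does not stop treatment enters neither the AE tables nor any planned laboratory summary.

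**The case against.** A reader might infer more than this: that falls below normal and immune-mediated toxicity go untabulated, or that the laboratory outputs look in the wrong direction for the blood-count risks. The documents do not support that.

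- CTCAE grade rises as neutrophils and platelets fall, and Protocol 8.10 grades every laboratory variable that CTCAE covers. The maximum-grade shift therefore captures neutropenia and thrombocytopenia, the principal count risks. The by-visit tables also show the minimum (SAP 6.1), and abnormal results are flagged in listings.
- Immune-mediated events appear in the SOC and preferred-term tables and in the grade tables, with no frequency threshold. Liver elevations have their own tables in SAP 11.4, and QTc categories are in SAP 11.6.
- The protocol asks for thyroid tests to be collected but specifies no thyroid table. Protocol Table 9 omits them as well, and Protocol 8.10 does not mention them. SAP 11.4 says that all laboratory results will be listed, which may include them.
- Maximum might mean worst category rather than highest value, and the mock-ups are in a separate document that could settle this.

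The first three points stand and limit the finding. The last does not remove it. On a Low/Normal/High scale both ends can be abnormal, so worst category has no meaning until the SAP says how a patient with both a low and a high value is classed. A by-visit minimum shows the lowest value in the arm, not how many patients fell below normal. A mock-up document is also not the place to introduce or drop an output that the protocol requires.

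**Conclusion.** The point holds as three bounded gaps. The AESI omission is the clearest: a protocol-required output is absent from the SAP and not declared in SAP 13. The loss is the grouped count per compound, not the individual events. The shift rule misses patient-level falls below the reference range for tests without a CTCAE grade for low values, and it hides direction for tests graded both ways. The thyroid gap is confined to changes that Protocol 6.4.6 keeps out of AE reporting. It rests on that section's general commitment to summarise mandated tests, not on a specific thyroid requirement.

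No number of patients can be attached to any of these, because the documents give no abnormality or event rates for these outputs. The laboratory conclusion assumes that maximum means the highest value, and all three assume that the separate mock-ups do not already supply the outputs. The efficacy analyses are unaffected. The changes should be made because the safety objectives depend on these tables and the correction is small.

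**What to change.** 1. **SAP 11.3:** add AESI summaries and listings for each compound, by arm, category, preferred term and CTCAE grade. Use the Protocol 6.9.6 and Appendix H categories for MEDI4736 with or without tremelimumab, and the Protocol 6.3 categories for AZD5069. State that AZD9150 has none. Fix the preferred terms in each category, and define the immune-related AE set in SAP 11.9 from the same list. If the sponsor decides against AESI outputs, declare and justify that in SAP 13.
2. **SAP 11.4:** report reference-range shifts from baseline to the minimum and, separately, to the maximum post-baseline value. Report the worst CTCAE grade separately for the low and high directions.
3. **SAP Table 9 and 11.4:** add TSH, free T3 and free T4, and include them in the by-visit and shift tables.

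The cost is SAP wording, a term list and a few more tables from data already collected. The main drawback is output volume.

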### **Hy's law**

The following summaries by treatment group will include number (%) of patients who have elevated ALT, AST, and total bilirubin during the study:

ALT > 3x – <= 5x, > 5x – <=10x and > 10x Upper Limit of Normal (ULN) during the study

AST > 3x – <=5x, > 5x – <=10x and > 10x ULN during the study

Total bilirubin >2x ULN during the study

Individual patient data where ALT or AST plus total bilirubin are elevated (ALT ≥ 3xULN and total bilirubin ≥ 2xULN or AST ≥ 3xULN and total bilirubin ≥ 2xULN) at any time will be listed. Individual patient profile plots will display values of ALP, ALT, AST, total bilirubin, and GGT relative to ULN by study day for patients where any individual where ALT or AST plus total bilirubin are elevated (ALT ≥ 3xULN and total bilirubin ≥ 2xULN or AST ≥ 3xULN and total bilirubin ≥ 2xULN) at any time.

Plots of ALT and AST vs. total bilirubin by treatment group will also be produced with reference lines at 3xULN for ALT, AST, and 2xULN for total bilirubin. In each plot, total bilirubin will be on the vertical axis.

## Statistical Analysis Plan

### **Neutrophil-to-Lymphocyte Ratio**

A series of line plots will present the mean neutrophil-to-lymphocyte ratio over time (Day -7, Day 0 and every 2 weeks subsequently) and by treatment arm for both Part A and Part B. For Part A, a single line plot will show the mean neutrophil-to-lymphocyte ratio for all AZD9150 + MEDI4736 doses combined and for all AZD5069 + MEDI4736 doses combined. For Part B, 2 separate line plots will be provided that display the mean neutrophil-to-lymphocyte ratio over time by treatment group—one for anti-PD-(L)1 naive patients and one for anti-PD-(L)1 pre-treated patients. If necessary, a slight lateral offset will be used to prevent data points from different treatment groups with similar mean neutrophil-to-lymphocyte ratios from being obscured.

A corresponding series of tables will summarize the descriptive statistics (mean, StD, median, mix, max) for the neutrophil-to-lymphocyte ratio by study visit and treatment arm for both Part A and Part B.

## Statistical Analysis Plan

**Table 9**                      **Routine laboratory safety assessments**

| Haematology/Haemostasis (whole blood) | Clinical Chemistry (serum or plasma) |
|--|---|
| B-Haematocrit (HCT)                          | S/P-Albumin                                 |
| B-Haemoglobin (Hb)                           | S/P-Alkaline phosphatase                    |
| B-Platelet count                             | S/P-ALT                                     |
| B-Red blood cell count                       | S/P-AST                                     |
| B-White blood cells                          | S/P-Bilirubin, total                        |
| B-WBC differential (%)                       | S/P-Bilirubin, direct                       |
| B-Absolute neutrophil count                  | S/P-Bilirubin, indirect                     |
| B-Absolute lymphocyte count                  | S/P-GGT                                     |
| B-Mean corpuscular volume                    | S/P-Calcium, total                          |
| B-Mean corpuscular haemoglobin concentration | S/P-Creatinine                              |
|  | S/P-Glucose                                 |
|  | S/P-LDH                                     |
| Urinalysis (dipstick)                 | S/P-Magnesium                               |
| U-Specific gravity                           | S/P-Phosphate                               |
| U-pH   | S/P-Potassium                               |
| U-Bilirubin                                  | S/P-Sodium                                  |
| U-Blood                                      | S/P-Total protein                           |
| U-Glucose                                    | S/P-Urea nitrogen                           |
| U-Ketones                                    | S/P-Chloride                                |
| U-Protein                                    | S/P-Bicarbonate                             |
| U-Color                                      | S/P-Uric acid                               |
| U-WBC/HPF and RBC/HPF (macroscopic)          | S/P-Creatine phosphokinase                  |
| U-Appearance                                 | S/P-Cholesterol                             |
|  | S/P-Triglycerides                           |
| Coagulation                           | S/P-C-reactive protein                      |
| PT (sec)                                     |   |
| aPTT (sec)                                   |   |
| INR  |   |
| Fibrinogen                                   |   |
| Haptoglobin                                  |   |

Abbreviations: ALT=alanine aminotransferase; aPTT=activated partial thromboplastin time; AST=aspartate aminotransferase; B=blood; GGT=gamma-glutamyl transpeptidase; INR=international normalised ratio; HPF=high power field; LDH=lactate dehydrogenase; P=plasma; PT=prothrombin time; RBC=red blood cell count; RBC/HPF= red blood cells per high power field; S=serum; WBC/HPF= white blood cells per high power field.

